4.1.2 Long-term Treatment Period

Subjects who complete the safety and efficacy evaluations at week 12, have not discontinued investigational product, and who in the opinion of the investigator may benefit from continued treatment, will have the option to continue treatment in an exploratory long-term treatment period. The long-term treatment period will provide opportunity to explore the long-term safety and efficacy of continued treatment with efavaleukin alfa for up to 40 weeks (total of up to 52 weeks of treatment). During the long-term treatment period, subjects will continue to receive their assigned blinded dose of investigational product (placebo or efavaleukin alfa) at the week 12 visit. The exception will be placebo nonresponder subjects, who are defined as those randomized to placebo during the induction period and who failed to achieve clinical response at week 12. These placebo nonresponder subjects will be assigned in a blinded manner to receive [REDACTED] µg [REDACTED] dose during the long-term treatment period. Treatment assignment during the long-term treatment period will be done by interactive response technology (IRT) based on the modified Mayo score using the locally read endoscopy subscore assigned by the investigator (refer to Section 6.1.1.2).

During the long-term treatment period, subjects will be assessed for worsening of disease activity, defined by a partial Mayo score of ≥ 4 with an increase from week 12 in rectal bleeding subscore to ≥ 2 and/or an increase from week 12 in stool frequency subscore to ≥ 2 . It is recommended that the investigator should determine whether a subject should discontinue investigational product based on worsening of disease activity, either based on the partial Mayo criteria above or their clinical judgement.

Subjects who were nonresponders at week 12, and who have an inadequate response by [REDACTED] will be discontinued from further investigational product administration in long-term treatment period.

Inadequate response is defined by failure to achieve a 2-point reduction and 25% improvement in partial Mayo score compared to the partial Mayo score at screening (and a minimum partial Mayo score of ≥ 5 points) at [REDACTED]

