Efficacy evaluations during the long-term treatment period will include the total and partial Mayo score, fecal calprotectin, and corticosteroid use. The modified Mayo score (including endoscopy) and mucosal biopsies for histopathology will be assessed at the week 52/ early termination visit.

If a subject discontinues investigational product prior to week 52, the subject will be encouraged to maintain the planned scheduled assessments through week 52 (Table 1-3).

If the subject discontinues the study completely prior to week 52, the subject should complete an early termination (ET) visit (ie, week 52 visit procedures) which must be scheduled to allow for [REDACTED]

[REDACTED] If a subject undergoes ET soon after having their week 12 endoscopy, the need for an ET endoscopy should be discussed with the Amgen physician.

Subjects who complete the week 52 endoscopy and who, in the opinion of the investigator, may benefit from continued treatment, will be assessed for eligibility to roll over into the Phase 2 Long Term Extension Study (20210210).

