**Duration of IP Exposure (Overall Study):**

The duration of IP exposure (overall study) will be derived as the last date of IP administration prior to EOS plus 13 days (14 day window - 1), EOS, or data cutoff date, whichever occurs first, minus the day of first IP administration + 1 day.

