**Exposure-Adjusted Adverse Events:**

The exposure for the analysis of exposure adjusted TEAEs and serious TEAEs for the overall study period is defined for each subject as **(EOS – first dose date +1)**.

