**End of Study Date:**

EOS for each subject is the date recorded on the EOS eCRF page.

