Exposure-adjusted subject incidence rate of TEAEs, serious TEAEs, TEAEs leading to discontinuation from investigational product, fatal TEAEs, treatment-related TEAEs, treatment-related serious TEAEs, treatment-related TEAEs leading to discontinuation from investigational product, treatment-related fatal TEAEs, and TEAEs of interest will be presented for the overall study period.

Overall summary of subject incidence of TEAEs and by preferred term and worst severity grade will be provided by anti-AMG592 and Anti-IL-2 antibody status.

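### Overall-study rates of TEAEs leading to IP discontinuation (and of injection site reactions, if reported) are divided by time to end of study, which counts follow-up after IP has stopped and understates the rate per time at risk

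*SAP*

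**What the plan says.** SAP 5.1 (Exposure-Adjusted Adverse Events) gives a single formula, "EOS – first dose date +1", with no separate version for any category of event. SAP 5.3 adds that "EOS for each subject is the date recorded on the EOS eCRF page", so the clock ends when the subject leaves the study, not when dosing ends.

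SAP 9.6.1 then asks for "Exposure-adjusted subject incidence rate of TEAEs, serious TEAEs, TEAEs leading to discontinuation from investigational product, fatal TEAEs", continues with the treatment-related versions, and closes the list with "treatment-related fatal TEAEs, and TEAEs of interest will be presented for the overall study period". The same section names injection site reaction among the possible events of interest.

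The protocol provides for time in study without IP:
- Protocol 4.1.2: "If a subject discontinues investigational product prior to week 52, the subject will be encouraged to maintain the planned scheduled assessments through week 52". Protocol 4.1.1 says the same for stopping during induction, and Protocol 7.1 stresses keeping such subjects on study where safe and feasible.
- Week 12 nonresponders with an inadequate response at a later (redacted) visit "will be discontinued from further investigational product administration in long-term treatment period" (Protocol 4.1.2).

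SAP 5.1 also defines dosing time: "The duration of IP exposure (overall study) will be derived as the last date of IP administration prior to EOS plus 13 days", or EOS or data cutoff if earlier, counted from the first dose. SAP 9.6.7 summarises the duration of IP exposure, but the adverse event rates do not use it.

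**The concern.** A rate per unit of exposure should divide events by time in which they could have happened. TEAEs are counted up to EOS (SAP 5.1), so for TEAEs in general numerator and denominator match.

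They do not match for a TEAE leading to IP discontinuation. After the last dose, follow-up adds to the denominator but can add nothing to the numerator. An injection site reaction is almost the same case: it could appear shortly after the last injection, but not months later. The surplus time comes largely from subjects who never have the event and stop IP for another reason, such as lack of efficacy.

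The wording also invites misreading. In its duration definitions SAP 5.1 uses exposure to mean dosing time, while in the adverse event definition it means total follow-up. A reader of the table would naturally take the figures as rates per time on drug. If columns carry different shares of off-IP time, the comparison between them shifts as well as the level.

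**Working it through.** The plan states no adverse event rate, IP discontinuation rate or off-IP time, so there is no figure of its own to reproduce. For events that occur only on IP the numerator is the same under both denominators, hence

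EOS-based rate / on-IP rate = (total on-IP time) / (total time to EOS).

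**Inputs from the documents.** On-IP time runs to last dose + 13 days (SAP 5.1). Maximum time in study is 61 weeks (Protocol 4.4). Subtracting 5 weeks of screening, 12 of induction and 40 of long-term treatment leaves 4, so EOS is at most about 56 weeks after first dose (day 393).

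**Assumptions, not in the documents.** The share stopping early, when they stop, and the share of stoppers who stay to week 52.

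**One subject.** Last dose at week 12, followed to week 52: on-IP time 84 + 13 + 1 = 98 days; EOS time 364 + 1 = 365 days. Ratio 98/365 = 0.27.

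**One column.** Let q be the share stopping early, t their mean on-IP weeks and s the share of stoppers staying to week 52. Other stoppers leave 4 weeks after stopping, and completers have 52 weeks on IP with EOS at week 54.

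Ratio = [qt + (1-q)52] / [q(52s + (1-s)(t+4)) + (1-q)54]

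- q = 0.2, t = 24, s = 0: 46.4/48.8 = 0.95
- q = 0.4, t = 16, s = 0.5: 37.6/46.8 = 0.80
- q = 0.6, t = 8, s = 1: 25.6/52.8 = 0.485

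Over q = 0.2-0.6, t = 8-24 and s = 0-1 the ratio lies between 0.95 and 0.49. It is below 1 in every case.

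**Two columns with the same true on-IP rate, 20% against 50% stopping.** Others are on IP to day 364 with EOS at day 393.

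| Stop at | Stoppers stay to day 393 | Stoppers leave 4 weeks after stopping |
|---|---|---|
| Week 24 | (324.8/393)/(266/393) = 1.22 | (324.8/353.6)/(266/294.5) = 1.02 |
| Week 12 | (308/393)/(224/393) = 1.38 | (308/336.8)/(224/252.5) = 1.03 |

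**Direction.** With constant hazards and a true on-IP rate ratio of 2.0 (0.10 against 0.05 per year), stopping for other reasons was set at 0.8 per year in one arm and 0.3 in the other. With 0%, 50% and 100% of stoppers staying, the EOS-based ratio is:
- 1.94, 1.73 and 1.58 if the active arm has the higher rate of other stopping;
- 2.05, 2.25 and 2.42 if it has the lower.

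If other stopping is equal (0.4 per year in both arms), it is 1.99 to 1.96.

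**Column structure.** SAP 5.1 (Actual Treatment Group in the Overall Study Period) forms columns from induction plus long-term treatment. The placebo-overall column therefore holds placebo responders who continue, and also placebo subjects who stop in induction or do not continue. Continuing placebo nonresponders form a separate column. Suppose all randomised arms behave alike: 15% stop at week 6, 80% of the rest continue, 35% of those are responders, half of continuing nonresponders stop at week 24, and half of all stoppers stay to week 52. The ratios are then 0.73 (active), 0.66 (placebo overall) and 0.81 (placebo then active). With response at 20-50% and staying at 0-100%, they are 0.58-0.92, 0.42-0.91 and 0.72-0.93.

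**The case against.** The choice of EOS was deliberate. The SAP revision history for Amendment 1 records that the exposure-adjusted definition was changed to take in all events up to EOS, and a rate per time in follow-up is interpretable. This stands for TEAEs in general, but it does not cover an event that needs ongoing IP.

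The effect may be small. The protocol only encourages subjects to stay and provides an early termination visit for those who leave. Termination for futility (SAP 11) may have cut off-IP follow-up further. Both points stand and belong in the range.

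The output is descriptive (SAP 9.1), and other tables give context: induction incidence without exposure adjustment (SAP 9.6.1), IP discontinuation with reasons (SAP 9.2) and duration of IP exposure (SAP 9.6.7). This stands and limits the importance. Nothing in the documents makes this rate the main long-term tolerability figure.

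Two points of wording also weigh. The SAP 5.1 definition names only TEAEs and serious TEAEs; applying it to the other categories rests on their being TEAEs with no other denominator given. And SAP 9.6.1 lists events of interest as possibilities, so injection site reactions may not be reported this way.

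A reader might infer that placebo carries little off-IP time and efavaleukin alfa much, so that the comparison flatters the drug. The documents do not support this. Placebo overall includes early placebo stoppers, and when all arms behave alike it was the most understated column (0.66 against 0.73 for active).

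**Conclusion.** The point holds at minor severity. As written, the overall-study rate of TEAEs leading to IP discontinuation (all and treatment-related) is understated per time at risk whenever subjects are followed after IP stops. The same is essentially true of injection site reactions, if reported.

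The size cannot be read from the documents. Under the assumptions shown, the EOS-based rate is about 0.95 down to 0.49 of the on-IP rate. Distortion between columns is possible, because stopping IP depends on response and placebo subjects are split by later treatment. It runs from about 1.02-1.03 if stoppers leave promptly to about 1.2-1.4 if all stay and the columns stop at 20% against 50%. Its direction is not determined, and early termination may shrink it.

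EOS-based time is sound for the other TEAE categories. The induction incidence tables and the efficacy analyses are unaffected.

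**What to change.** In SAP 5.1, state that for TEAEs leading to IP discontinuation, treatment-related TEAEs leading to IP discontinuation, and injection site reactions (if reported as an event of interest), the denominator is the Duration of IP Exposure (Overall Study) already defined there. Keep EOS-based time for all other TEAE categories. Footnote the two denominators and label the EOS-based rates as per subject-year of follow-up.

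The cost is a sentence in the SAP and a footnote. No new data are needed, since SAP 9.6.7 already calls for the duration of IP exposure. The drawback is two denominators in one table. The change also leaves on-IP time after a subject's first injection site reaction in the denominator; that is a separate question, which it does not settle.

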#### **9.6.2            Laboratory Test Results**

Change and percent change from baseline in select clinical laboratory test results will be summarized over time by each treatment group. In addition, shift tables, from baseline to the worst on-study laboratory toxicity based on the CTCAE version 5 or later will be presented.

Subject incidence of worst post-baseline of eosinophils counts and percentages by the laboratory normal range will be tabulated by treatment group.

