9.4.2.3.2 Laboratory Test Results

The analyses of safety laboratory endpoints will include summary statistics over time by each treatment group. Shifts in grades of safety laboratory values between baseline to the worst on-study value will be presented.

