### **9. Statistical Methods of Analysis**

#### **9.1 General Considerations**

All categorical variables will be summarized using the number and percent of subjects falling into each category and all continuous variables will be summarized using mean, standard deviation (SD), median, first quartile (Q1), third quartile (Q3), minimum, maximum, and number of subjects with observations.

Nominal p-values will be reported for the primary, secondary, and select exploratory efficacy endpoints, with no adjustment for multiplicity.

Safety endpoints will be summarized descriptively, including treatment-emergent adverse events and serious adverse events in the induction period, clinically significant changes in laboratory values and vital signs, and incidence of antidrug antibodies.

Exposure-adjusted treatment-emergent adverse events and serious adverse events will be summarized for the overall study period.

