#### **9.6 Safety Analyses**

##### **9.6.1 Adverse Events**

The Medical Dictionary for Regulatory Activities (MedDRA) version 27.0 or later will be used to code all events categorized as adverse events to a system organ class and a preferred term. The severity of each adverse event will be graded using CTCAE criteria version 5.0 or later ([Appendix A](#)). Summaries of adverse events during the induction adverse event exposure period will be presented by actual treatment received in the induction period. Exposure-adjusted subject incidence rates for the overall study period will be presented by actual treatment received in the overall study.

Subject incidence of all TEAEs, serious TEAEs, TEAEs leading to discontinuation from investigational product, fatal TEAEs, treatment-related TEAEs, treatment-related serious TEAEs, treatment-related TEAEs leading to discontinuation from investigational product,

treatment-related fatal TEAEs, and TEAEs of interest that occur in the induction adverse event exposure period will be summarized.

Subject incidence of treatment-emergent adverse events identified by COVID-19 standardized MedDRA queries and serious adverse events occurring on or after the COVID-19 infection that occur in the induction adverse event exposure period will also be summarized.

Subject incidence of events of interest (standardized MedDRA queries and/or Amgen Medical Queries) that occur in the induction adverse event exposure period will also be summarized according to their categories and preferred term. Events of interest could include but are not limited to Hypersensitivity, Tachyarrhythmias, Tachypnea, Hematopoietic Cytopenia, Drug Reaction with Eosinophilia, Leucocyte Changes, Infection and Infestation, Cytokine Release Syndrome, and Injection Site Reaction. Number of episodes and duration of treatment-emergent injection site reactions will be further summarized by treatment group.

In addition, summaries of TEAEs and serious TEAEs occurring in at least 5% of the subjects in any treatment arm and serious TEAEs occurring in at least 2% of the subjects in any treatment arm by preferred term that occur in the induction adverse event exposure period will be provided in descending order of frequency.

Summaries of TEAEs and serious TEAEs that occur in the induction adverse event exposure period will be tabulated by system organ class, preferred term, and grade. An overall summary of adverse events by toxicity grade will be provided.

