### Appendix B. Analytical Windows

Since the actual visit for a subject may not exactly coincide with their scheduled visit date, to allow for variations in scheduling, the following visit windows will be used to assign evaluations to a most appropriate nominal visit for analysis and summarization. Furthermore, there will be no gaps between visit windows in order to include as many data points as possible for summarization.

If more than one actual visit (including the unscheduled visits) falls within the same defined window, the visit closest to the target day with non-missing data will be considered for analysis. If two actual visit dates are at the same distance from the target day, the latest visit with non-missing data will be considered for analysis.

If more than one evaluation falls on the same date and time for laboratory results, then the value with the smallest accession number will be used.

Analysis visit windows for selected assessments are included in tables below. For remaining assessments, no visit window will be applied.

Study Day Window				
Analysis Visit	Target Day	Vital Signs	Chemistry, Hematology, Urinalysis	Fecal Calprotectin, hsCRP
6 to 24 hour Post Dose	1	1-2		
48 to 96 hour Post Dose	3	3 - 5		
		6 - 19	2 - 22 (Chemistry and Hematology only)	
		20 - 26		
		27 - 35	23 - 42 (Chemistry and Hematology) 2 - 42 (Urinalysis)	2 - 42
		36 - 49		
		50 - 63	43 - 70	43 - 70
		64 - 77		

	78 - end of induction date	71 - end of induction date	71 - end of induction date
	(end of induction date + 1) - 105		
106 - 119		(end of induction date + 1) - 126	
120 - 133			
134 - 147		127 - 154	
148 - 161			
162 - 175		155-182	(end of induction date + 1) - 210 (Fecal Calprotectin only)
176 - 189			
190 - 203		183-210	
204 - 217			
218 - 231		211-238	
232 - 245			
246 - 259		239-266	211 - 308 (Fecal Calprotectin only)
260 - 273			
274 - 287			
288 - 301			
302 - 315			
316 - 329			
330 - 343			

	344 - 357		
	358 - 378	267-378	309 - 378 (Fecal Calprotectin only)

Analysis Visit	Target Day	Study Day Window			
		Anti-efavaleukin alfa antibody	Partial Mayo Score, Physician Global Assesment (PGA)	Lymphocyte subset	Weight, Modified Mayo Score, endoscopy and Geboes score
	2 - 22	2 - 19	2 - 19		
		20 - 26	20 - 26		
	23 - 42	27 - 35			
		36 - 49	27 - 49		
	43 - 70	50 - 63			
		64 - 77			
	71 - end of induction date	78 - end of induction date	50 - end of induction date	2 - end of induction date	
		(end of induction date + 1) - 126			
		127 - 154			

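### SAP 9.6.2 takes the worst laboratory grade and worst eosinophil category over the whole study, so follow-up length and the week 12 placebo switch confound the between-arm comparison in these tables

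*SAP*

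**What the plan says.** SAP 9.6.2 plans two categorical laboratory displays. For graded tests, "shift tables, from baseline to the worst on-study laboratory toxicity based on the CTCAE version 5 or later will be presented". For eosinophils, "Subject incidence of worst post-baseline of eosinophils counts and percentages by the laboratory normal range will be tabulated by treatment group". Protocol 9.4.2.3.2 has the same rule: "Shifts in grades of safety laboratory values between baseline to the worst on-study value will be presented". None of these sentences gives an end date, and SAP Section 5 does not define on-study as the induction period. SAP 9.1 lists "treatment-emergent adverse events and serious adverse events in the induction period, clinically significant changes in laboratory values and vital signs", where the reference to induction follows the adverse event terms and is not attached to the laboratory values. The laboratory windows in SAP Appendix B run to day 378.

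Adverse events are handled differently in SAP 9.6.1. Crude incidence is confined to induction: "Summaries of adverse events during the induction adverse event exposure period will be presented by actual treatment received in the induction period". The longer period is adjusted: "Exposure-adjusted subject incidence rates for the overall study period will be presented by actual treatment received in the overall study".

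SAP 6.2 assigns the Safety Analysis Set by actual treatment received. SAP 5.1 gives separate definitions of actual treatment for induction, for the long-term period and for the overall study. Section 9.6.2 does not say which one applies.

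**The concern.** A worst value is a maximum over draws, so it cannot improve as draws are added. The number of draws depends on what happens after randomization. Under Protocol 4.1.2, long-term treatment is optional and rests on the investigator's view of benefit. Week 12 nonresponders whose response is still inadequate at a later (redacted) week "will be discontinued from further investigational product administration in long-term treatment period".

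The assigned drug can also change. Placebo nonresponders who continue receive efavaleukin alfa from week 12 (Protocol 4.1.2 and 6.1.1.2). If 9.6.2 is read with induction grouping, their later values, drawn on active drug, count against placebo and could hide a signal. If it is read with overall grouping, the placebo/efavaleukin group consists only of people who entered the long-term period. Neither reading gives the randomized comparison.

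This matters because SAP 9.6.1 names cytopenia, leukocyte changes and drug reaction with eosinophilia as events of interest. The worst-value tables are the only place in 9.6.2 where individual outlying values are counted by category.

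**Working it through.** The documents give no figure for this point, so there is none to reproduce. The group size is 240/4 = 60.

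**Inputs from the documents**
- Chemistry and hematology windows in induction: 4 (SAP Appendix B: days 2-22, 23-42, 43-70, and 71 to end of induction). Protocol Table 1-2 also shows 4 hematology marks.
- Long-term period: 7 windows in SAP Appendix B, and 9 hematology marks in Protocol Table 1-3 as extracted. The totals are therefore 4 + 7 = 11 or 4 + 9 = 13. Both are carried through because the extracted table may be broken.

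**Assumptions (not in the documents)**
- Chance p of an abnormal value per draw: 2%, with 1% and 5% as a range.
- Within-subject correlation rho: 0, 0.2 or 0.5.
- Share of an arm entering and completing the long-term period: 60% in one arm, 85% in another.
- No drug effect.

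**Formulas**
- Independent draws: P(n) = 1 - (1 - p)^n.
- Correlated draws (beta-binomial): P(n) = 1 - B(a, b + n)/B(a, b), with B the beta function, a = p(1 - rho)/rho and b = (1 - p)(1 - rho)/rho.
- Arm proportion with entry share e: e × P(long) + (1 - e) × P(4). The difference between arms is (0.85 - 0.60) × [P(long) - P(4)].

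**Results at p = 2%** (differences from unrounded values)

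| rho | 4 draws | 11 draws | 13 draws | Arm difference, 60% v 85% |
|---|---|---|---|---|
| 0 | 7.8% | 19.9% | 23.1% | 3.0 to 3.8 points |
| 0.2 | 5.9% | 10.8% | 11.7% | 1.2 to 1.4 points |
| 0.5 | 4.1% | 5.9% | 6.2% | 0.4 to 0.5 point |

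Worked line for rho = 0: P(4) = 1 - 0.98^4 = 7.8% and P(11) = 1 - 0.98^11 = 19.9%, so 0.25 × (19.9 - 7.8) = 3.0 points.

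In 60 subjects, 3.0 to 3.8 points is 1.8 to 2.3 people, and 0.4 to 0.5 point is 0.2 to 0.3 of a person.

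**Range.** For the same entry shares, p = 1% gives 1.6 to 2.1 points (independent) or 0.2 to 0.3 (rho 0.5). With p = 5% the figures are 6.1 to 7.5 or 1.0 to 1.2. A contrast of 30% v 100% entry is conceivable when the placebo/efavaleukin group, all entrants by definition, is set against another group. At p = 2% it gives 8.5 to 10.7, 3.4 to 4.0 and 1.2 to 1.5 points for rho 0, 0.2 and 0.5.

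**Effect of an early termination draw.** If everyone who does not continue has one more draw at an early termination visit, P(5) = 1 - 0.98^5 = 9.6%. The independent-draw difference becomes 0.25 × (19.9 - 9.6) = 2.6 to 0.25 × (23.1 - 9.6) = 3.4 points.

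**After restriction to induction.** All who complete induction have the same 4 scheduled draws. With no drug effect, every arm has the same expected proportion among them (7.8% independent, 4.1% at rho 0.5), and long-term entry contributes a difference of 0.

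The calculation covers follow-up length only. The effect of counting active-drug values under placebo depends on the drug effect and cannot be sized from the documents.

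**The case against.** The strongest reply is that the damage is limited, and much of it stands.

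- **Other tables cover the 12-week comparison.** SAP 9.6.2 also summarizes change and percent change over time by group, which does not accumulate draws. The events of interest are counted within induction under SAP 9.6.1. A reader might infer that the randomized 12-week laboratory comparison is missing altogether. It is not. What is missing is that comparison for worst grade and worst eosinophil category. The other tables do not fill this gap: averages can miss individual outliers, and Protocol 8.4.3 generally keeps laboratory findings without clinical significance out of the adverse event record.
- **Stopping drug does not stop draws.** Protocol 4.1.1, 4.1.2 and 7.1 encourage subjects who stop treatment to keep attending. Those who leave the study have an early termination visit, which includes hematology and chemistry. Long-term entry does not require response. So draws do not simply follow response, and 4 is not a firm count for someone who does not continue. Attendance after stopping is still not compulsory, so follow-up can differ between arms.
- **Differential retention is not shown.** The documents give no entry shares. SAP Section 11 reports termination for futility, which offers no support for large response differences between doses. The argument rests on what the plan allows.
- **The tables are descriptive and follow the protocol.** A whole-study worst value also serves to catch late abnormalities. That is a reason to keep it as a second display, but it does not make it suitable for comparing arms.

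**Conclusion.** The point holds as a gap in specification that confounds two tables. As written, SAP 9.6.2 gives worst-value proportions that mix drug effect with follow-up length and, for placebo, with a change of drug at week 12. The treatment grouping is left open.

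More draws can only raise a subject's worst value. The size between arms is unknown. It is about 3 to 4 points under an assumed 2% per-draw risk, independent draws and 60% v 85% entry, and about 0.5 point with correlation 0.5. It is close to zero if entry shares are similar.

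Two stronger readings are not supported. A reader might set 4 draws against 11 and infer a 2.3- to 2.7-fold inflation (43.1%/18.5% at p = 5%, 10.5%/3.9% at p = 1%). That compares two individual subjects under independent draws. It would describe arms only if nobody in one arm continued and everybody in another did. A reader might also infer that the arms cannot be compared on laboratory safety at all. The visit-wise summaries and induction adverse event tables show that they can.

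**What to change.** In SAP 9.6.2, state that the between-arm shift and eosinophil tables use the worst value within the induction adverse event exposure period, by actual treatment received in induction. Both definitions already stand in SAP 5.1.

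That period can end the day before the week 12 dose when dosing follows the endoscopy. The sentence should therefore say that a pre-dose draw on the day of the first long-term dose counts as induction.

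Keep the whole-study worst-value tables as a separate descriptive display by overall treatment group. Show the number of draws or subject-time for each group, and note that the placebo/efavaleukin group contains long-term entrants only.

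The cost is a short SAP change and one additional set of tables, with no new data. One limit remains: subjects who leave during induction will still have fewer than 4 draws.
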